3.4 Study Treatments

3.4.1 Methods of Assigning Subjects to Treatment Group

Eligible subjects will be randomized in a 1:1:1 ratio at Visit 2 (Baseline) and will receive either placebo, SPN-812 ER 200 mg/day, or SPN-812 ER 400 mg/day.

Allocation of study treatment will occur centrally via an interactive web response system (IWRS) using a randomization schedule to determine the kit assignment for each subject being randomized

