3.5 Sample Size and Power Considerations

Seventy-two subjects per treatment group in the ITT population will yield 90% power at a significance level of 0.05 (two-sided) using a two-sample t-test with equal allocation to the treatment

groups. This assumes an effect size of 0.547, observed in the comparison of SPN-812 200 mg and placebo in the SPN-812 Phase IIb study (based on the CFB to endpoint in the ADHD-RS-IV total score). A total of 300 subjects (100 subjects in each of the three treatment groups) will be randomized to account for an anticipated 27.9% of randomized subjects not completing the study.

4 Definitions and Derivations

1. Baseline: Unless specified otherwise, baseline is defined as the non-missing value collected most recent to and before the time of the very first dose of the SM.
2. The study day (DY) is calculated as Visit date minus Reference date + 1 day if the visit date occurs on or after the reference date or Visit date minus Reference date if the visit date occurs before the Reference date, where the Reference date is defined as the first dose date (DY=1)
3. The change from baseline at a given Visit = observed value at that Visit minus observed value at baseline
4. ADHD-RS-5 total score =sum of scores for the 18 behaviors
5. ADHD-RS-5 Inattention subscale score = sum of scores for the first 9 behaviors
6. ADHD-RS-5 Hyperactivity/Impulsivity Subscale score = sum of scores for the last 9 behaviors
7. Conners 3-Parent Reported score: Composite T-score calculated by averaging over the 6 domains
8. Conners 3-Parent Reported score: T-score for individual domain: inattention, hyperactivity/impulsivity, aggression, executive functioning, learning problems, and relationships
9. Conners 3-Self Reported score domains: Composite T-score over the 5 domains
10. Conners 3-Self Reported score domains: inattention, hyperactivity/impulsivity, aggression, learning problems, and relationships
11. WFIRS-P score=average of all 50 items
12. WFIRS-P subscale scores: average of items of following 6 subdomains: Family, School (learning and behavior), Life Skills, Child's Self-Concept, Social Activities, and Risky Activities
13. PSI-4-SF: score=sum of all 36 items
14. PSI-4-SF: subscale scores: sum of items of following 3 subdomains: parental distress (PD), parent-child dysfunctional interaction (P-CDI), and difficult child (DC)

5 Study Variables

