The ADEFF1 analysis dataset will be used for programming the primary analysis table and will contain variables for Subject ID, BASE (Baseline (Visit 2)), AVAL (values at Visit 3 –Visit 10), CHG (for CFB), ITT Flag variable, Treatment, and other necessary variables to be created. For each subject there will be nine records associated with nine visits: Baseline and Visit 3 - Visit 10. The ADEFF2 analysis dataset will be created based on MI assuming MNAR for sensitivity analysis and MI assuming MAR for secondary analyses. The ADEFF2 will contain 100 imputations of each record of each visit for the variables in ADEF1 with IMPUTNR variable.

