6.13.1 Analysis of Primary Endpoint

The primary efficacy variable, change from baseline in ADHD-RS-5 Total Score to Week 8 (EOS), will be analyzed using a Mixed Model for Repeated Measures (MMRM), which assumes that missing data are missing at random (MAR). The model will include fixed effect terms for baseline ADHD-RS-5 Total Score, age group, treatment, visit, and treatment-by-visit interaction as independent variables. The model parameters will be estimated using restricted maximum likelihood method with unstructured variance-covariance matrix and Kenward-Roger approximation to estimate denominator degrees of freedom. In case there is a convergence problem in the MMRM model with the unstructured variance covariance matrix, the first (co)variance structure which does not have convergence problem will be used for the analysis from the following ordered list: 1) Toeplitz 2) Autoregressive of order 1 3) Compound symmetry.

The adjusted mean (LS Mean) of CFB to EOS for ADHD-RS-5 Total Score for each treatment group (Placebo, SPN-812 ER 200 mg and SPN-812 ER 400 mg) will be presented, along with the corresponding standard error. Each of the treatment groups (SPN-812 ER 200 mg and 400 mg) will be compared with the Placebo. The p-values, Least Squares (LS) of treatment means, differences between the LS treatment means and placebo, and 95% confidence intervals for the treatment differences will be computed.

To maintain the Type I error rate at 5% level, a sequential testing ([Westfall et al 1999](#)) of the null hypotheses H_{01} : No treatment mean difference between SPN-812 ER 400 mg group and placebo group and H_{02} : No treatment mean difference between SPN-812 ER 200 mg group and placebo group

will be performed. If H_{01} is not rejected, then H_{02} will not be tested and the conclusion will be that neither dose groups are efficacious. If H_{01} is rejected, then H_{02} will be tested. If H_{02} is rejected then it will be concluded that both SPN-812 ER 400 mg and SPN-812 ER 200 mg are superior to placebo. If H_{01} is rejected and H_{02} is not rejected then it will be concluded that only SPN-812 ER 400 mg is superior to placebo.

The summary of primary analysis will be presented in Table 14.2.1.1.

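### All three fallback covariance structures for the primary MMRM assume equal variance at every visit, so if one is used the Week 8 standard error may be biased in either direction

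*SAP*

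**What the plan says.** The primary endpoint in SAP section 6.13.1 is the Week 8 change from baseline in ADHD-RS-5 Total Score. The MMRM adjusts for baseline score and age group and is fitted by "restricted maximum likelihood method with unstructured variance-covariance matrix and Kenward-Roger approximation to estimate denominator degrees of freedom".

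The fallback has one trigger: "In case there is a convergence problem in the MMRM model with the unstructured variance covariance matrix". The first structure that converges is then taken, in this order: "1) Toeplitz 2) Autoregressive of order 1 3) Compound symmetry". None is described as heterogeneous, and no robust (sandwich) variance is named. Section 6.6.1 names PROC MIXED as the software. There these three labels mean a common variance at all visits, and the heterogeneous forms are separate types (TOEPH, ARH(1), CSH).

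The model has eight repeated visits. Section 6.1 describes the analysis dataset thus: "For each subject there will be nine records associated with nine visits: Baseline and Visit 3 - Visit 10". That is eight post-baseline records per subject.

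On variability, section 3.5 gives only a standardised effect: "This assumes an effect size of 0.547, observed in the comparison of SPN-812 200 mg and placebo in the SPN-812 Phase IIb study". The SAP contains no SD by visit and no within-subject correlations.

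**The concern.** The test that matters is at a single visit, Week 8. A homogeneous structure estimates one variance from all eight visits and applies it to that one. If the residual spread at Week 8 is larger than average, the model-based standard error is too small and the test rejects too often. If it is smaller, the standard error is too large and power is lost. Kenward-Roger is a small-sample adjustment within the fitted structure and does not correct a structure that is wrong.

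There is a reason to expect growth. The response is change from baseline, adjusted for baseline. If the correlation with baseline decays over time, the residual variance of that response rises across visits even when the raw score has the same SD at every visit.

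The result carries weight because the 400 mg comparison gates the 200 mg comparison (section 6.13.1), and both gate the key secondary endpoints (section 6.14.1). An error in the fallback test would pass down the hierarchy.

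**Working it through.** **The plan's own figure.** Section 3.5 states: "Seventy-two subjects per treatment group in the ITT population will yield 90% power at a significance level of 0.05 (two-sided". With effect size 0.547, the noncentral t power is 89.9% at 71 per group and 90.3% at 72. Then 72/(1 − 0.279) = 99.9, so 100 per group. The sample size reproduces; it does not bear on the fallback.

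**Parameter counts for 8 visits.** Unstructured: 8 × 9/2 = 36. Toeplitz 8, AR(1) 2, CS 2. TOEPH, ARH(1) and CSH replace one variance by eight, so each adds 7.

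**Simple calculation (complete data, large sample).** The SD patterns are assumptions.

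- Pooled SD = √(mean of SD² over 8 visits)
- Ratio r = model SE / true SE at Week 8 = pooled SD / Week 8 SD
- Type I error = 2 × [1 − Φ(1.96 r)]

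For eight equally spaced SDs with step s, the mean of SD² is (mean SD)² + 5.25 s².

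| SD, Week 1 to Week 8 | Mean of SD² | Pooled SD | r | Type I error |
|---|---|---|---|---|
| 10 to 12.5 | 127.23 | 11.28 | 0.902 | 7.7% |
| 9 to 13 | 122.71 | 11.08 | 0.852 | 9.5% |
| 8 to 14 | 124.86 | 11.17 | 0.798 | 11.8% |
| constant | – | – | 1.000 | 5.0% |
| 13 to 10 | 133.21 | 11.54 | 1.154 | 2.4% |

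**Power in the falling case.** Take 0.547 as standardised by the Week 8 SD (an assumption), with 72 per group. The expected z is 0.547 × √(72/2) = 3.282. Correct-SE power is Φ(3.282 − 1.960) = 90.7%. With the SE overstated by 1.154 it is Φ(3.282 − 2.262) = Φ(1.020) = 84.6%.

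**Fuller calculation.** Each structure was fitted to an assumed true covariance by minimising expected Gaussian deviance, and the model SE was compared with the true SE at Week 8. Two correlation patterns were assumed: 0.85^lag and 0.35 + 0.5 × 0.8^lag. The ranges cover both patterns and all three structures. Dropout is monotone and completely at random.

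| SD pattern | Complete, 72 per arm | 27.9% dropout, 100 per arm |
|---|---|---|
| 9 rising to 13 | 9.4–9.5% | 9.6–11.7% |
| 7 rising to 14 | 12.8–13.2% | 13.8–16.1% |
| 8 rising to a plateau at 13 | 7.7–8.6% | 8.2–9.7% |
| flat 12 | 5.0% | 4.7–6.4% (Toeplitz 5.0%) |
| 9 up to 13, then 11 at Week 8 | 3.5–4.5% | 3.8–4.9% |
| 13 falling to 10 | 2.3–2.4% | 2.0–3.4% |

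The departures in the flat row under dropout come from AR(1) or CS misfitting the correlation, not from unequal variance. This calculation omits the baseline and age-group covariates and small-sample terms.

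**Is growth plausible?** Assume raw scores with constant SD (set to 1), correlation ρ^t between baseline and visit t, and one common baseline slope b, equal to the mean of ρ^t over t = 1 to 8. The residual variance at visit t is 1 + b² − 2bρ^t, and its average over visits is 1 − b². For ρ = 0.85, b = 0.515, the average is 0.734 and the Week 8 value is 0.985. So r = √(0.734/0.985) = 0.86 and type I error is 9.1%. The same steps give 6.5% at ρ = 0.70, 8.0% at 0.80, 10.4% at 0.90 and 12.2% at 0.95. If the raw correlation is the same at every lag, ρ^t is replaced by a constant and the mechanism vanishes.

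**The case against.** A reader might infer that these fallbacks necessarily understate the Week 8 standard error and inflate type I error. The documents do not support that. Equal variance alone does not set the direction of the bias, and the SAP gives no visit SDs from which to tell. Over the assumed patterns, type I error runs from about 2.0% to 16.1%. With constant variance Toeplitz, the first fallback, is at 5.0%. The decay argument makes growth plausible, but its correlations are assumed too. A plateau after the three-week titration is as credible as a steady rise and gives smaller figures than the steeper linear cases.

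A reader might also infer that the primary analysis as planned is at fault. It is not: with the unstructured matrix the problem does not arise. The fallback needs a convergence failure, which is unlikely with 36 covariance parameters, fixed weekly visits and about 300 subjects.

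Cross-checks also exist. The placebo-based sensitivity analysis (section 6.13.2) fits ANCOVA to Week 8 change alone and so pools no variance across visits. Section 6.13 calls for descriptive summaries by visit, and the MMRM output will be listed. A distorted standard error would probably be noticed, but none of these replaces the primary test.

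These objections limit the point to a minor, conditional one. They do not remove it: the rule as written offers no structure that allows the variance to differ by visit.

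**Conclusion.** The point holds in conditional form. If the unstructured model fails to converge, every listed fallback fixes a common variance across visits, and the Week 8 standard error is then biased whenever Week 8 residual variance departs from the cross-visit average. Under the simple calculation, type I error is about 7.7% to 11.8% for linearly rising SD, 5% for constant SD (Toeplitz), and about 2.4% with lost power for SD falling from 13 to 10. All these SD patterns are assumptions. Because it depends on an unlikely trigger and on an unknown variance pattern, the severity is minor; correcting it is a cheap improvement.

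**What to change.** In section 6.13.1, put heterogeneous Toeplitz (TOEPH), heterogeneous AR(1) (ARH(1)) and heterogeneous compound symmetry (CSH), in that order, ahead of or in place of the three present structures, and keep Kenward-Roger. The ordered, first-to-converge rule can stay as it is.

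A sandwich standard error should be at most a last resort, for the case where only a homogeneous structure converges. It cannot be combined with Kenward-Roger, so the SAP would then have to name its degrees-of-freedom method. Requiring it for every fallback would conflict with the specified method and is not needed when the structure already allows unequal variances.

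The cost is a change of SAP wording and up to seven more variance parameters in the fallback model, which makes convergence of that model slightly harder. The change should be made before database lock and unblinding, since a fallback chosen afterwards would not be credible.

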6.13.2 Sensitivity Analysis

The sensitivity analysis assumes that missing ADHD-RS-5 Total Scores are missing not at random (MNAR), that is, the probability that an observation is missing may depend on its underlying unobserved value. (For example, the probability of missing ADHD-RS-5 Total Score at Week 8 is not related to the observed ADHD-RS-5 Total Score at visit 9). Placebo-based multiple imputation will be used to fill in missing values. This approach may be considered “worst-case” sensitivity analyses as it assumes that after discontinuation, subjects from the active treatment arms would adopt the outcome model estimated from the placebo arm. The placebo-based imputation will be implemented by adopting the following three steps.

- 1) SAS PROC MI (SEED=220877) is applied to the input dataset containing all by-visit ADHD-RS-5 Total Score during the baseline, titration, and maintenance period. Multivariate imputation will be carried out by the fully conditional specification (FCS) method. One hundred (100) multiply-imputed datasets will be created. SAS® PROC MI with the MNAR statement will be implemented by using the following SAS code.

```
PROC MI DATA= EFF NIMPUTE=100 SEED=220877 OUT=MNAROUT
  CLASS TREATMENT;
  VAR BASE WK1– WK8(EOS);
  FCS REG;
  MNAR MODEL (BASE WK1– WK8 (EOS))/MODELOBS= (TREATMENT='A');
  RUN;
```

In the above SAS code, EFF denotes the efficacy data set, Base, WK1– WK8 are analysis values of ADHD-RS-5 total at baseline and each of treatment weeks from Week 1 (at Visit 3) to Week 8 (at Visit 10), and treatment = ‘A’ denotes Placebo.

2. For each of the multiply-imputed data sets, CFB to EOS will be computed. For each imputation, the CFB will be analyzed using ANCOVA model, which will include fixed effect terms for treatment and baseline ADHD-RS-5 Total Score as a covariate. Each of the treatment groups (SPN-812 ER 200 mg and 400 mg) will be compared with the Placebo. The LS means of treatment groups, differences between the LS means of treatment groups and placebo, 95% confidence intervals around the differences and p-value will be computed.
3. Finally, to combine estimates (LS means, treatment LS mean differences, 95% CI around the difference and p-value) from the 100 datasets, SAS® PROC MIANALYZE will be used.

The summary of sensitivity analysis will be presented in Table 14.2.1.2. The corresponding full SAS output will be presented in Listing 16.1.9.2.

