6.14.2.3 ADHD-RS-5 Hyperactivity/Impulsivity and Inattention Subscales

The change from baseline to EOS in ADHD-RS-5 Inattention and the change from baseline to Week 8 (EOS) in Hyperactivity/Impulsivity subscales will be analyzed using ANCOVA model with fixed effects for treatment, age group and baseline as a covariate. Each of the treatment groups (SPN-812 ER 200 mg and 400 mg) will be compared with the Placebo. The p-values, LS means of treatment groups, differences between the LS means and placebo will be presented. The summary of this analysis will be presented in Table 14.2.2.3.

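### The placebo-based MNAR sensitivity analysis leaves age group out of both its imputation model and its ANCOVA, although the primary MMRM adjusts for it

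*SAP*

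**What the plan says.** - **Primary analysis (SAP 6.13.1).** "The model will include fixed effect terms for baseline ADHD-RS-5 Total Score, age group, treatment, visit, and treatment-by-visit interaction as independent variables". Missing scores are taken to be missing at random.
- **Sensitivity analysis, imputation (SAP 6.13.2, step 1).** "Placebo-based multiple imputation will be used to fill in missing values". The CLASS statement holds only treatment. The variable list is "VAR BASE WK1– WK8(EOS" (closing bracket omitted here), that is, the baseline and weekly total scores and nothing else.
- **Sensitivity analysis, model (SAP 6.13.2, step 2).** Change from baseline is fitted by ANCOVA in each of the 100 imputed data sets, "which will include fixed effect terms for treatment and baseline ADHD-RS-5 Total Score as a covariate".
- **Subscales of the same instrument (SAP 6.14.2.3).** The ANCOVA has "fixed effects for treatment, age group and baseline as a covariate".
- **Per-protocol analysis of the primary endpoint (SAP Supplementary Analyses).** The ANCOVA has treatment and baseline only.
- **Age categories.** Only the subgroup section (6.15) gives any: 6-9 and 10-11 years. Section 6.13.1 uses the term without defining it.

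**The concern.** The sensitivity analysis is there to show how far the primary result depends on the missing-at-random assumption. A reader will judge that by setting Table 14.2.1.2 beside Table 14.2.1.1. The comparison is clearest when the two analyses differ in as little as possible besides that assumption.

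Section 6.6.1 explains that MMRM deals with missing scores by conditioning on earlier observations and on covariates that may carry information about both missingness and outcome. Apart from baseline score, age group is the only baseline covariate of that kind in the primary model, and the sensitivity analysis drops it at both steps. The SAP anticipates that 27.9% of randomized subjects will not complete, so the comparison is likely to be read closely.

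**Working it through.** **Side by side**

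| Feature | Primary (6.13.1) | Sensitivity (6.13.2) | Avoidable difference? |
|---|---|---|---|
| Missing-data assumption | MAR | MNAR, placebo-based | No, this is the purpose |
| Model form | MMRM | ANCOVA on imputed data | No, usual after multiple imputation |
| Baseline score | Yes | Yes | None |
| Age group in analysis model | Yes | No | Yes |
| Age group in imputation model | Not applicable | No | Yes |

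Section 6.14.2.3 fits age group in an ANCOVA on ADHD-RS-5 subscale scores, so the move to ANCOVA does not by itself explain the omission.

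**Sample size.** The SAP states no figure for age group. Its nearest figure is the sample size (3.5): effect size 0.547, two-sided 0.05, 90% power. A two-sample t-test gives 71.2, rounded up to 72 per arm, with power 90.3% at 72. Inflating for non-completion gives 72 / (1 - 0.279) = 99.9, so 100 per arm and 300 in all. These figures reproduce, and they do not depend on age group.

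**Precision.** Let R2 be the share of residual variance that age group explains; its value is assumed. The standard error with the term, relative to without it, is sqrt(1 - R2).

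- R2 = 0.01: sqrt(0.99) = 0.995, a reduction of 0.5%.
- R2 = 0.04: sqrt(0.96) = 0.980, a reduction of 2.0%.

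Over a wider range, leaving the term out makes the standard error larger by 1/sqrt(1 - R2) - 1, which is 1.0% at R2 = 0.02, 2.6% at 0.05 and 5.4% at 0.10. If 0.547 is read as the effect size without age group, power at 72 per arm is 90.3% without the term. With it, power is 90.6%, 90.9%, 91.7% and 93.0% at R2 of 0.01, 0.02, 0.05 and 0.10.

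**Shift in the estimate.** A simulation of 4,000 trials used 100 per arm, complete Week 8 data, a true difference of -0.547 in residual SD units and 40% of subjects in one age category. All of these settings except the 100 per arm and the effect size are assumptions.

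| R2 | Mean difference without age group | With age group | SD of within-trial gap |
|---|---|---|---|
| 0 | -0.548 | -0.548 | 0.009 |
| 0.02 | -0.545 | -0.546 | 0.022 |
| 0.05 | -0.550 | -0.549 | 0.034 |

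The average estimate does not move. The standard error is about 0.141, so a typical gap within one trial is 0.022 / 0.141 = 0.16 standard errors at R2 = 0.02 and 0.034 / 0.141 = 0.24 at R2 = 0.05. A shift of 0.16 from z = 1.96 gives z of 2.12 or 1.80, which takes a two-sided p of 0.05 to about 0.034 or 0.072.

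The simulation has no missing data, so it does not measure what leaving age group out of the imputation model would do. That depends on how age relates to dropout and outcome, and the SAP gives no figure for either.

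**The case against.** **The models differ anyway.** This stands. With age group added, an ANCOVA on 100 imputed data sets is still being compared with a repeated-measures model. A reader might infer that the fix isolates the MNAR assumption, and it does not. It removes only the difference that the analyst is free to remove.

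**Treatment plus one baseline covariate is the plan's usual ANCOVA.** This is also true. CGI-I, Conners 3, WFIRS-P and PSI-4-SF all take that form, and the subscale model is the exception. But those are other instruments with no primary model to match. Both other inferential models for ADHD-RS-5 scores in the ITT population, the primary MMRM and the subscale ANCOVA, carry age group.

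**The SAP never promises a one-assumption comparison.** Correct. It describes a worst-case style analysis and does not commit to the primary covariates. The point is therefore one of good practice and not a contradiction. The protocol might also hold a reason for the choice, although none appears in the SAP.

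**Two stronger readings that the document does not support.** A reader might infer that the omission biases the sensitivity result. Under 1:1:1 randomization with complete data it does not, and nothing in the SAP shows bias with missing data. A reader might also treat the per-protocol ANCOVA as the same fault. That analysis uses a different population, defined in 6.3.4 as having no missing ADHD-RS-5 assessments, so it was never a test of the missing-data assumption alone.

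**Conclusion.** The point holds as a minor, avoidable inconsistency. Age group is in the primary model and absent from both steps of the sensitivity analysis on the same score, with no stated reason. A gap between the two tables could partly reflect this.

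The expected size is small: a standard error lower by about 0.5 to 2% with the term, assuming that age group explains 1 to 4% of residual variance. With complete data there is no shift in the average estimate, and the sample size is unaffected. The effect through the imputation model cannot be quantified from the SAP. Nothing here suggests that the sensitivity analysis is invalid or that the trial's conclusion would change.

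**What to change.** In SAP 6.13.2:

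1. Add age group to the CLASS and VAR statements of the PROC MI code, so that imputation and analysis use the same covariates. Changing the ANCOVA alone would leave the imputation blind to a term in the analysis model.
2. Add age group as a fixed effect in the step 2 ANCOVA.
3. Define the age categories for the primary model and use the same ones here. They are assumed to be the 6-9 and 10-11 years given for subgroups in 6.15; the sponsor should confirm this.

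Optionally, and only for consistency, add the term to the per-protocol ANCOVA of the primary endpoint. If age group was left out on purpose, one sentence giving the reason would do instead.

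The cost is a few words of SAP text and one extra term in each of two programs, using a variable already in the primary model. No new data and no extra subjects are needed. The change should be made before database lock.
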